Proposed Treatment/Study Plan:

Standard treatment post allogeneic transplant is supportive care only.

Statistical Considerations:

Preliminaries

This is a randomized, controlled phase III trial to compare azacitidine (AZA) maintenance to standard of care in patients with high risk AML/MDS who have undergone an allogeneic stem cell transplant (allotx). Patients will be randomized fairly between azacitidine and standard of care. Starting at 40 to 100 days post allotx, patients randomized to the azacitidine arm will receive 32 mg/m² for five consecutive days of each 28 day cycle and the maximum treatment will be 12 cycles. Each cycle will consist of approximately 28 days, allowing the possibility that treatment within a cycle may be delayed for up to 4 weeks due to organ toxicity or hematologic toxicity.

Group sequential design

The primary outcome for treatment evaluation will be relapse-free survival (RFS) time. A null historical RFS time of 6 months will be assumed. The goal will be to

test the hypothesis that azacitidine provides at least a 50% improvement in $m =$ median RFS, from 6 to 9 months. An accrual rate of 6 patients per month will be assumed. A two-sided group sequential procedure will be used [2] with overall type I error .05 and power .80 to detect the alternative $m = 9$ months, with up to 2 interim tests and one final test, including both outer bounds for superiority and inner bounds for futility. All tests will be based on a standardized log rank statistic, and will be performed using the following cut-offs.

No. Events	Outer Z-score cut-off to reject the null hypothesis (Superiority)	Inner Z-score cut-off to accept the null hypothesis (Futility)
71	+/- 3.7103	+/- .2438
142	+/- 2.5114	+/- 1.0268
214	+/- 1.993	+/- 1.993

The number of patients accrued (sample size) required to achieve the necessary numbers of events required by the group sequential tests will be between 213 and 246 (all to be enrolled at MDACC).

The randomization will be stratified by disease (AML, MDS, biphenotypic leukemia).

Secondary outcomes

Additional outcomes that will be recorded and analyzed will include overall survival (OS) time, acute (grade 3 or 4) graft-versus host disease, organ toxicity and hematologic toxicity.

Data analyses

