All adverse events will be cross-tabulated with treatment arm, and the rates compared using a Fisher exact test. Unadjusted RFS and OS times will be estimated using the Kaplan-Meier method. Covariate adjusted comparisons will be done using a Cox model or other appropriate time-to-event regression model to be determined by preliminary goodness-of-fit analyses.

Where Will Participants Be Enrolled:

Only at MDACC

Is this an NCI-Cancer Therapy Evaluation Protocol (CTEP)? No

Is this an NCI-Division of Cancer Prevention Protocol (DCP)? No

Estimated Accrual:

Total Accrual at MDACC: 246
Estimated monthly accrual at MDACC: 6

Accrual Comments:

Do you expect your target population to include non-english speaking participants? No

Location of Treatment:

This protocol is performed on an Outpatient basis.

Length of Stay: What is the length & frequency of hospitalization?

No hospitalization is planned under this study.

Return Visits: How often must participants come to MDACC?

Daily for 5 days of each 28 day-cycle (for drug administration). Once prior to starting the drug and once weekly for 2 weeks after drug administration is completed for labs. Pts are to receive azacitidine for no more than 1 year after the first dose.

Home Care: Specify what, if any, treatment may be given at home.

There is no home care under this study. However, local physicians, should they agree to administer the drug as prescribed here, will administer azacitidine.

Name of Person at MDACC Responsible for Data Management: [name]

Prior protocol at M. D. Anderson:

Has the Principal Investigator ever had a clinical or behavioral protocol at MDACC that accrued patients?
Yes

Data Monitoring Committee:

Is treatment assignment randomized? Yes

Is this a blinded or double-blinded study? No

Does this Protocol need data safety monitoring? Yes

Provide the name of the data safety monitoring board (DSMB) monitoring this protocol:
MDACC DMC

Does this protocol have a schedule for interim and final analysis? Yes

Please describe:

We plan to have interim analyses when accrual reaches 71 and 142 patients, and a final analysis when we complete enrollment, as described in the statistical section.

Radiation Safety:

Does this study involve the administration of radioisotopes or a radioisotope labeled agent?	No
Is the radioactive compound (or drug) FDA approved and/or commercially available?	No

Investigational New Drugs:

Does this protocol require an IND? No

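### The stated lower sample size of 213 patients cannot supply the 214 events that the final test requires

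*Combined protocol and SAP*

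**What the plan says.** Under Statistical Considerations, Group sequential design, the plan sets out a log-rank design for RFS: "A two-sided group sequential procedure will be used [2] with overall type I error .05 and power .80". The aim is to "test the hypothesis that azacitidine provides at least a 50% improvement in $m =$ median RFS, from 6 to 9 months". The boundary table places the three tests at 71, 142 and 214 events.

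The next sentence gives the number of patients "required to achieve the necessary numbers of events required by the group sequential tests" and says that it "will be between 213 and 246 (all to be enrolled at MDACC"). It does not say how either end of that range was obtained. No minimum follow-up and no loss rate are stated.

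Two later sections bear on this. Estimated Accrual gives a single figure: "Total Accrual at MDACC: 246". The Data Monitoring Committee section schedules the interim analyses at 71 and 142 patients accrued, and the final analysis at the completion of enrolment. The same two counts appear in the boundary table as events.

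**The concern.** The range is offered as the number of patients that will produce the required events, yet its lower end is below the largest event count in the table directly above it. This conflict needs no modelling, because the event count can never exceed the number of patients.

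A sample-size sentence is what a study team consults when deciding whether accrual may close. A reader who takes 213 as sufficient would have a trial that cannot reach its own final trigger. Even a total slightly above 214 would need an event in almost every patient, and therefore years of follow-up that the plan does not mention.

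**Working it through.** **Inputs from Group sequential design.** Two-sided type I error 0.05 and power 0.80. Control median: "A null historical RFS time of 6 months will be assumed". Alternative median 9 months, so the hazard ratio is 6/9 = 0.667 if RFS is exponential. "An accrual rate of 6 patients per month will be assumed". Looks at 71, 142 and 214 events with the printed outer and inner cut-offs.

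**Assumptions that the plan does not state.** Exponential RFS; no loss to follow-up; 1:1 allocation, read from "Patients will be randomized fairly between azacitidine and standard of care".

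**Step 1: reproduce the event count.** A fixed design needs 4(1.96 + 0.842)²/(ln 1.5)² ≈ 191 events. Integrating the log-rank process numerically through the printed boundaries, with drift |ln 0.667|/2 per root event, gives:
- power 0.801 at 71/142/214 events with the futility bounds applied;
- two-sided type I error 0.050 with futility ignored and 0.044 with it applied;
- 213.04 final events for exactly 80% power.

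So 214 is a sound event target, and 213 is close to the same quantity rounded the other way. Equal spacing from the first look also gives 3 × 71 = 213.

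**Step 2: compare patients with events.** Maximum events from 213 patients = 213, which is below 214. This holds for any survival curve and any length of follow-up.

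**Step 3: expected events over time.** With N patients, let a = min(t, N/6). Expected events at month t are the sum over the two arms of 3 × [a − (e^(−λ(t−a)) − e^(−λt))/λ], where λ = ln 2/6 = 0.1155 or ln 2/9 = 0.0770.

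For N = 213, accrual ends at month 213/6 = 35.5:
- Null (6/6): 6 × [35.5 − (1 − 0.0166)/0.1155] ≈ 162.
- Alternative (6/9): 3 × [35.5 − (1 − 0.0166)/0.1155] + 3 × [35.5 − (1 − 0.0650)/0.0770] ≈ 81 + 70 = 151.

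The same formula gives the following (null / alternative):

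| N | Events when accrual ends | Month of the 214th event |
|---|---|---|
| 213 | 162 / 151 | never |
| 215 | 164 / 153 | 70 / 84 |
| 220 | 169 / 158 | 55 / 63 |
| 230 | 179 / 167 | 48 / 53 |
| 246 | 195 / 183 | 45 / 48 |

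With 213 patients, expected events are 200 / 192 after 12 further months and 212 / 210 after 36. With 246, accrual ends at month 246/6 = 41, so the 214th event is expected 45.1 − 41 ≈ 4 months (null) to 48.4 − 41 ≈ 7 months (alternative) later.

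**Step 4: could 213 be enrolment at an interim look?** With accrual still open, expected enrolment is 118 / 126 at 71 events and 193 / 204 at 142 events. This depends on the unstated assumptions. With 1% loss per month, enrolment at 142 events is about 214 under the alternative. With 2% it is about 211 (null) to 224 (alternative). With no loss and 9-month medians in both arms it is about 215.

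**Step 5: sensitivity of 246 to loss.** With a constant loss rate g per month, a share λ/(λ + g) of patients is ever observed to have an event. At g = 0.01 the ceiling is 246 × 0.1155/0.1255 ≈ 226 (null), or 123 × 0.1155/0.1255 + 123 × 0.0770/0.0870 ≈ 222 (alternative). At g = 0.02 it is 246 × 0.1155/0.1355 ≈ 210 under the null, below 214. The loss rates are illustrations, because the plan gives none.

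**The case against.** The best defence is that the discrepancy is one unit and changes nothing. The event requirement for 80% power is about 213 and the looks are spaced in steps of 71, so 213 and 214 may be one quantity rounded two ways. A test at 213 events would have power of 79.99% against 80.1%. Estimated Accrual fixes the total at 246, and no section gives a rule for closing at 213. All of this stands, and it limits the harm. It does not rescue the sentence. If 213 is an event count, it has been printed as a patient count, and a patient minimum equal to the event target requires every patient to have an event.

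A reader might go further and infer that the final test cannot be carried out. The documents do not support that: planned accrual is 246, which is expected to reach 214 events without loss, and a log-rank test can be computed at 213 events. Only the combination of 213 patients and a 214-event trigger is impossible.

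A reader might also infer that 213 corresponds to no look of the design. That is not established. It nearly equals the unrounded final event requirement, and modest loss to follow-up would bring enrolment at the second look close to 213. The plan does not say where the figure came from.

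**Conclusion.** The lower limit of 213 is wrong as printed. That conclusion rests only on the table and on one event per patient. The explanation that an event requirement was entered as a patient count is plausible but is an inference.

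The size of the shortfall rests on exponential RFS, 1:1 allocation and no loss. On those terms, 213 patients would have about 151 to 162 events when accrual ends, which is 71% to 76% of 214. The practical consequence is limited because the stated total is 246, and on the same terms that total is adequate.

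A related conflict matters more in practice. If the final analysis is done when enrolment is complete, as the Data Monitoring Committee section has it, even 246 patients are expected to give only about 183 to 195 events, or 86% to 91% of 214. The event-based and accrual-based timings cannot both apply.

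**What to change.** In Group sequential design, delete 213 and replace the range with wording such as: 246 patients, unless the trial stops at an interim test; the final test is done at 214 events, expected about 4 to 7 months after accrual ends (assuming exponential RFS and no loss to follow-up). If losses are expected, state the rate and recompute the timing, since step 5 shows that 246 is sensitive to it.

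If enrolment at the interim tests is also quoted (about 118 to 126 at 71 events and 193 to 204 at 142 events), label it as resting on the same assumptions.

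In the Data Monitoring Committee section, restate the interim and final analyses in events, so that they match the boundary table.

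The cost is one sentence in each section. The boundaries, the event counts and the total accrual of 246 do not change.

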THE UNIVERSITY OF TEXAS

Protocol Abstract Page

Randomized controlled study of post-transplant azacitidine for prevention of acute myelogenous leukemia and myelodysplastic syndrome relapse
(VZ-AML-PI-0129)
2008-0503

Core Protocol Information

Study Chairman:	[name]
Department:	Stem Cell Transplantation and Cellular Therapy
[contact]
Unit:	423
Full Title:	Randomized controlled study of post-transplant azacitidine for prevention of acute myelogenous leukemia and myelodysplastic syndrome relapse (VZ-AML-PI-0129)
Protocol Phase:	Phase III
Version Status:	Terminated 08/20/2018
Version:	29
Document Status:	Final

Abstract

Objectives:

Primary

1. To compare in a randomized controlled fashion the relapse-free survival of acute myelogenous leukemia and myelodysplastic patients treated with post transplant maintenance azacitidine.

Secondary

1. To compare survival of patients receiving azacitidine with that of untreated controls.
2. To document toxicity of maintenance therapy with azacitidine.

Rationale: (Be as concise as possible)

Allogeneic hematopoietic stem cell transplantation for patients with high-risk acute myelogenous leukemia (AML) and myelodysplastic syndrome (MDS) is associated with high failure rates. Although this form of treatment is associated with a high complete remission rate, the major cause of failure is disease relapse, which usually occurs early after transplantation.

Here we propose to use maintenance treatment with low doses of 5-azacitidine (Vidaza) after transplantation. The rationale for the choice of low doses of azacitidine is as follows: recovering marrows after transplantation are very susceptible to myelosuppression, and higher doses are not well tolerated; in addition, we are not seeking a cytotoxic effect, but hope to induce hypomethylation and myeloid cell differentiation and possibly, magnify the graft-versus-leukemia effect. We have defined the safety of a dose at 32 mg/m² for 5 days, repeated at 28 day cycles, and now plan to evaluate this maintenance strategy in a randomized, controlled fashion.

Eligibility: (List All Criteria)

Inclusion:

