- 1) Patients with a diagnosis of AML (World Health Organization classification: >=20% blasts in the bone marrow and / or peripheral blood) or MDS (International Prognostic Scoring System intermediate-1 or higher) that at the time of allogeneic transplantation were in: - Induction Failure, relapsed disease or second or greater remission; patients in first complete remission that required more than 1 cycle of treatment to achieve the remission, or that have AML evolving from MDS, or that had the following abnormalities: FLT3 mutation, deletion of chromosome 5 or 7, MLL gene rearrangement, or more than or equal to 3 cytogenetics abnormalities. Patients with de novo or therapy-related MDS, CMML, or AML are also eligible, regardless of cytogenetics or molecular rearrangements.
- 2) Biphenotypic Leukemia that at the time of allogeneic transplantation was in induction failure, relapsed disease, first, second or greater remission.
- 3) Patients must be in complete remission post transplant.
- 4) Patient may be enrolled 40 to 100 days after transplant.
- 5) Age 18 to 75 years old.
- 6) Serum creatinine < 1.8 mg/dL or creatinine clearance greater or equal than 40 cc/min as defined by the Cockcroft-Gault Equation*. a. Males(mL/min):(140-age)*IBW(kg) / 72*(serum creatinine(mg/dl)) b. Females(mL/min):0.85*(140-age)*IBW(kg) / 72*(serum creatinine(mg/dl)).
- 7) Serum direct bilirubin < 1.5 mg/dL (unless Gilbert's syndrome).
- 8) SGPT <= 200 IU/ml unless related to patient's malignancy.
- 9) Be able to understand and sign informed consent.

Exclusion:

- 1) Active uncontrolled infection.
- 2) Presence of uncontrolled graft-versus-host disease.

- 3) Patients that underwent allogeneic transplantation as a treatment of graft failure.
- 4) Pregnancy or breast-feeding (women of childbearing potential, any female who has experienced menarche and who has not undergone surgical sterilization or is not post-menopausal with a positive serum pregnancy test).
- 5) Known or suspected hypersensitivity to azacitidine or mannitol.
- 6) Patients with advanced malignant hepatic tumors.

Is there an age limit? Yes

Why? Provide scientific justification:

The upper limit (75 years) is determined by physiologic limitations. The lower limit is dictated by the small numbers of patients that have the diseases studied here, a fact that prevents meaningful conclusions in the pediatric population.

Disease Group:

Leukemia

Treatment Agents/Devices/Interventions:

Azacitidine

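### Randomisation is stratified by disease but, as written, the primary log-rank tests are not; stratifying them costs little and helps if disease clearly predicts RFS

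*Combined protocol and SAP*

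**What the plan says.** Under Statistical Considerations, Group sequential design, the plan states "The randomization will be stratified by disease (AML, MDS, biphenotypic leukemia". No other stratification factor is named.

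The same section sets up a two-sided design "with up to 2 interim tests and one final test, including both outer bounds for superiority and inner bounds for futility", with "overall type I error .05 and power .80 to detect the alternative" of a 9-month median RFS against a null of 6 months. The looks are at 71, 142 and 214 events. On the statistic itself it says only: "All tests will be based on a standardized log rank statistic, and will be performed using the following cut-offs". The word for the scale of the statistic says that it is a Z-score; it does not say whether the score is summed over strata.

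The Data analyses section plans Kaplan-Meier estimates without adjustment, and then: "Covariate adjusted comparisons will be done using a Cox model or other appropriate time-to-event regression model to be determined by preliminary goodness-of-fit analyses". It names no covariates and does not link this model to the primary test.

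The document is headed "Protocol Abstract Page", so a fuller protocol text may exist.

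**The concern.** A factor is normally chosen for stratified randomisation because it is thought to affect outcome. If it does, an unstratified log-rank test has two drawbacks:

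- Its variance ignores the balance on disease that the randomisation has created. The test is then conservative, with true type I error below the planned level.
- Pooling groups with different baseline hazards pulls the unstratified hazard ratio towards 1, which lowers power.

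A test stratified on the same factor avoids both. What is at stake is efficiency and a clear specification. Neither test inflates type I error, and the 214 events and the cut-offs are not in question.

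**Working it through.** **1. The stated design reproduces.** With exponential RFS, medians of 6 and 9 months give HR = 6/9 = 0.667. A fixed design needs 4 × (1.960 + 0.842)² / (ln 1.5)² = 4 × 7.849 / 0.1644 ≈ 191 events. The plan's 214 is this figure inflated for the sequential bounds. Numerical recursion used information = events/4, looks at 71, 142 and 214 events, outer bounds 3.7103, 2.5114 and 1.993, and inner bounds .2438, 1.0268 and 1.993. It gives:

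- power 0.801 with futility followed (0.838 if ignored);
- two-sided type I error 0.0501 with futility ignored (0.0443 if followed).

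**2. The two statistics.** With O − E and V the usual log-rank score and variance:

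- unstratified: Z = (O − E) / √V, from one risk set over all patients;
- stratified: Z = Σₛ(Oₛ − Eₛ) / √(ΣₛVₛ), with risk sets formed within each disease s.

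**3. Simulation inputs.**

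- From the documents: N = 246, 6 patients per month, the three looks and their cut-offs with futility followed, control median 6 months, treatment HR 1/1.5 (or 1 for type I error).
- Assumed: 1:1 allocation in permuted blocks of 4 within disease; exponential RFS; the same treatment HR in every disease; AML/MDS/biphenotypic mixes of 60/35/5, 75/20/5 and 85/12/3%; biphenotypic hazard equal to AML.

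Scaling every exponential time by 1.5 also scales the pooled median by 1.5, so the pooled medians remain 6 and 9 months. Each scenario had 80,000 trials, and both tests were applied to the same trials. Standard errors are about 0.0014 for power, 0.0006–0.0010 for the paired difference and 0.0007 for type I error.

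**4. Power** (range over the three mixes; differences from unrounded values).

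| AML:MDS hazard ratio | Unstratified | Stratified | Effect of stratifying (points) |
|---|---|---|---|
| 1.0 | 0.793–0.798 | 0.786–0.789 | −0.7 to −0.9 |
| 1.25 | 0.790–0.793 | 0.786–0.790 | −0.3 to −0.4 |
| 1.5 | 0.781–0.788 | 0.787–0.790 | +0.2 to +0.8 |
| 2.0 | 0.749–0.773 | 0.789–0.790 | +1.7 to +3.9 |

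If MDS is the worse group, the effect is −0.2 to +0.6 point at a ratio of 0.67 and +0.9 to +3.4 at 0.5.

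**5. Type I error.** Unstratified: 0.045–0.046 at a ratio of 1.0, 0.041–0.044 at 1.5 and 0.036–0.040 at 2.0. Stratified: 0.045–0.046 throughout. Taking whichever of the two tests rejects gives 0.051–0.053.

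**6. Estimate.** At 214 events and a ratio of 2.0, the median Cox hazard ratio is 0.677–0.688 without disease strata and 0.666 with them, against a true 0.667.

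**7. Sensitivity to the biphenotypic group.** Separate runs of 8,000–20,000 trials set the MDS hazard to 1/r and the biphenotypic hazard to r relative to AML, with MDS shares of 20–45%. Stratifying then gains about 4–5 points at r = 2 and 9–14 at r = 3, and loses about half a point at r = 1. The step 4 figures are the more cautious ones.

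**8. Sparse stratum.** At a 5% share, biphenotypic events are about 0.05 × 71 ≈ 4, 0.05 × 142 ≈ 7 and 0.05 × 214 ≈ 11 at the three looks; at 3%, about 2, 4 and 6–7. Pooling these patients with AML in the analysis, compared with the unstratified test, costs 0.4–0.6 point at a ratio of 1.0, changes nothing at 1.25, and gains 0.5–1.1 at 1.5 and 2.0–4.3 at 2.0. If the biphenotypic hazard is really twice that of AML, pooling gives 0–0.5 point less power than three strata.

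**The case against.** The plan is silent; it does not say unstratified, and a stratified score can also be standardized. The unstratified test is valid, and leaving the choice open is nearly harmless (0.051–0.053 at worst). Every gain depends on a disease mix and a disease effect that appear nowhere in the documents. All patients are high risk and in remission after transplant, and the entry criteria define risk mainly by remission status at transplant and by genetics, so a two-fold AML:MDS difference is not evident. With a weak disease effect the unstratified test is slightly better. The planned Cox model could adjust for disease.

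Most of this stands, and it keeps the point small. That both tests fall a little below .80 is not evidence for the concern either, since the unstratified test does so even when disease has no effect.

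Two parts do not remove the point. The Cox model names no covariates and is not the primary test, so it does not fill the gap. And because the disease effect is unknown, there is a case for the test whose operating characteristics hardly depend on it: stratified power stays at 0.786–0.790 over ratios 1.0–2.0, while unstratified power ranges from 0.749 to 0.798.

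**Conclusion.** The concern holds as a low-severity improvement. As written, the only stratification factor is used in the randomisation and nowhere in the primary analysis. Stratifying risks less than 1 point of power if disease does not matter and gains about 2–4 points if AML and MDS hazards differ two-fold; the break-even lies between 1.25 and 1.5. It also holds type I error close to its design value and removes a small bias of the estimated hazard ratio towards 1.

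The sizes rest on assumed disease mixes, exponential RFS and a common treatment effect across diseases. Confidence is medium, because the disease effect is unknown and only abstract pages are available.

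**What to change.** State that the interim and final RFS tests all use the log-rank statistic stratified by the three disease groups used at randomisation, with event counts and cut-offs unchanged. Use the same strata in the supporting Cox model.

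If the biphenotypic group is expected to be very small, an acceptable alternative is two analysis strata (MDS; AML plus biphenotypic) at all three looks. It should be fixed in advance and described as such, since it departs from the randomisation strata.

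Two clarifications would help: list the Cox covariates, and name the stratum for CMML, which is eligible ("Patients with de novo or therapy-related MDS, CMML, or AML are also eligible, regardless of cytogenetics or molecular rearrangements") but not among the listed strata.

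The cost is wording only: no extra patients, events or cut-offs, and disease is known at randomisation. The downside is 0.7–0.9 point of power if disease is not prognostic (0.4–0.6 with the two-stratum version). The Core Protocol Information gives the version status as terminated, so a change made after unblinded comparisons should be labelled as not prespecified.

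### The primary log-rank test takes no account of disease status at transplant, so power falls below the stated .80 if status is at least moderately prognostic; stratifying the test is a cheap improvement

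*Combined protocol and SAP*

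**What the plan says.** In the Eligibility section, Inclusion 1 classifies AML and MDS patients by their state at transplant, listing "Induction Failure, relapsed disease or second or greater remission; patients in first complete remission that required more than 1 cycle of treatment" and then several further routes for first remission. Its last sentence also lets in de novo and therapy-related MDS, CMML and AML whatever the genetics. Inclusion 2 admits biphenotypic leukemia from induction failure through first or later remission. Inclusions 3 and 4 require every patient to be in complete remission after transplant and to enrol between days 40 and 100.

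Under Statistical Considerations, Group sequential design, "The randomization will be stratified by disease (AML, MDS, biphenotypic leukemia". The primary outcome is relapse-free survival, and "All tests will be based on a standardized log rank statistic"; no strata or covariates are named. The design has "overall type I error .05 and power .80 to detect the alternative" of 9 months and rests on one control figure: "A null historical RFS time of 6 months will be assumed".

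Data analyses adds covariate-adjusted comparisons by a Cox or other regression model. It leaves the model to goodness-of-fit checks, names no covariates, and does not connect the model to the cut-offs.

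**The concern.** Patients who reach transplant in relapse and patients who reach it in first remission may carry different hazards of relapse or death afterwards. When groups with different hazards are pooled in an unstratified log-rank, the higher-risk patients fail first. The risk mix in the two arms then drifts apart, and the observed hazard ratio moves towards 1. The test loses power even though the treatment effect within each group is unchanged. The planned test governs both the superiority and the futility decision at each look, so a diluted statistic makes a true effect harder to establish and a futility stop easier. At stake is whether the trial has the power it states.

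**Working it through.** **Inputs from the plan** (Group sequential design): median relapse-free survival 6 versus 9 months; looks at 71, 142 and 214 events; outer cut-offs 3.7103, 2.5114 and 1.993; inner cut-offs 0.2438, 1.0268 and 1.993; 6 patients per month; up to 246 patients. Allocation is read as 1:1.

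**Assumptions, not in the documents:** two status groups; exponential times within each; the poorer group's hazard 1 to 3 times the other's; 30%, 50% or 70% of patients in the poorer group; a treatment hazard ratio of 0.667 within each group; no dropout.

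**Step 1, the plan's own power.** The hazard ratio is 6/9 = 0.667, and ln 1.5 = 0.4055. A fixed design needs 4(1.960 + 0.842)²/0.4055² = 191 events. A single test at 214 events would have power Φ(0.4055 × √214/2 − 1.960) = Φ(1.006) = 0.843. Running the log-rank score process (drift ln 1.5, information = events/4) through the printed cut-offs gives upper crossings of 0.023, 0.438 and 0.340 at the three looks, a total of 0.801. Freedman's drift gives 0.791, and patient-level simulation with no status effect gives 0.797. The stated .80 is reproduced.

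**Step 2, adding status without changing the medians.** Take half the patients in the poorer group and a status hazard ratio of 2. The better group's control hazard λ solves 0.5e^(−6λ) + 0.5e^(−12λ) = 0.5. With x = e^(−6λ), x + x² = 1, so x = 0.618 and λ = 0.0802 per month. Control medians are 0.693/0.0802 = 8.6 months and half that, 4.3 months, in the two groups, and 6 months overall. Multiplying both hazards by 2/3 stretches the time scale by 1.5, so the overall azacitidine median is exactly 9 months. The plan's alternative, "median RFS, from 6 to 9 months", is therefore met in full.

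**Step 3, power through the printed cut-offs** (246 patients, blocks of 4, 20,000 simulated trials per cell, standard error about 0.003, half the patients in the poorer group):

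| Status HR | As planned | Test stratified by status | Randomization stratified by status, test not | Both stratified |
|---|---|---|---|---|
| 1 | 0.797 | 0.791 | 0.798 | 0.792 |
| 1.25 | 0.791 | 0.789 | 0.792 | 0.791 |
| 1.5 | 0.776 | 0.789 | 0.778 | 0.789 |
| 2 | 0.737 | 0.789 | 0.745 | 0.789 |
| 2.5 | 0.693 | 0.789 | 0.710 | 0.788 |
| 3 | 0.652 | 0.790 | 0.671 | 0.790 |

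A separate simulation with the medians held at 6 and 9 months gave 0.79, 0.78, 0.73 and 0.67 for the planned test at status hazard ratios 1, 1.5, 2 and 3, and 0.78 to 0.79 for the stratified test.

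The share in the poorer group matters less. With 30% poorer-status the planned test has power 0.780, 0.752 and 0.692 at ratios 1.5, 2 and 3. With 70% it has 0.777, 0.737 and 0.659. The stratified test stays at about 0.79.

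At ratio 2 with half the patients in the poorer group, the planned test regains .80 only with a within-status hazard ratio near 0.64 (power 0.811, azacitidine median 9.4 months).

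**Step 4, type I error.** From the printed cut-offs it is 0.0498 two-sided if the futility bounds are ignored and 0.044 with them. At status hazard ratio 2 the planned test's upper tail is 0.023, so there is no inflation.

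**The case against.** The strongest objection is that the size is entirely assumed. The documents give no case mix and no hazard ratio for status. Because all patients must be in remission at days 40 to 100, those who never remitted or had already relapsed are excluded, and only a residual effect of pre-transplant status remains. That stands. Up to a status hazard ratio of 1.5 the planned test loses only about 2 points, which is negligible in practice.

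The loss also requires 0.667 to be the hazard ratio within each status group. If it is the hazard ratio in the mixed population, the planned test keeps about .80. That stands too.

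The planned Cox model is a weaker answer, because it names no covariates and does not drive the decisions at the looks.

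A reader might infer several stronger points that the documents do not support:

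- **That eligibility makes status the chief risk marker, with first remission admitted only alongside extra risk features.** The last sentence of Inclusion 1 and the whole of Inclusion 2 are broader than that. Where features are required, they make first-remission patients high-risk as well.
- **That a single 6-month median presumes one homogeneous group.** A mixed population also has a median.
- **That chance imbalance in status undermines the comparison, most of all at 71 events.** With 123 per arm and half the patients poorer-status, one standard deviation of imbalance is √(0.5/123) = 6.4 points. At status hazard ratio 2 this shifts the log hazard ratio by 0.064 × 0.693 = 0.044, against a standard error of 2/√214 = 0.137, a ratio of 0.32. If roughly 127 patients are enrolled at the first look (an approximation), the ratio is about 0.06/0.237 = 0.26, which is smaller. This is ordinary sampling variation that the test already covers.
- **That stratifying the randomization is the remedy.** Alone it moves power only from 0.737 to 0.745 at ratio 2.

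**Conclusion.** The concern holds as a point about efficiency, not validity. Neither the primary log-rank nor the randomization uses disease status at transplant, and no other provision brings it into the decision test. With half the patients in the poorer group and a common within-status hazard ratio of 0.667, power is about 0.78 at a status hazard ratio of 1.5, 0.73 to 0.74 at 2, and 0.65 to 0.67 at 3. A status-stratified test holds about 0.79 throughout.

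It would be wrong to conclude that the trial is underpowered. The stated .80 reproduces, and whether it is lost depends on a status effect and a case mix that the documents do not give. The case for acting is the asymmetry: about half a point is given up if status is irrelevant, against about 5 points recovered at ratio 2 (0.789 − 0.737) and 14 at ratio 3 (0.790 − 0.652). This is a cheap improvement, not a defect that threatens the conclusions.

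**What to change.** In Group sequential design, pre-specify that the primary log-rank at all three looks is stratified by disease status at transplant, in two levels: in remission, or not in remission. Previously untreated MDS or CMML, which the last sentence of Inclusion 1 can admit, fits neither level naturally. Assign it in advance to a named level. Make the change before outcomes by arm are examined.

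As a secondary step, where randomization can still change, add the same factor to the randomization strata. Keeping three disease labels gives 3 × 2 = 6 cells; merging biphenotypic leukemia with AML gives 4. The merger is optional.

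The cost is a wording change, one more field in the randomization system if that step is taken, and about half a percentage point of power if status is not prognostic (0.797 to 0.791). No extra patients or procedures are needed, because status at transplant has to be established for most entrants under Inclusions 1 and 2.
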